3.9 Data to be collected, including potential effect modifiers and confounding factors

3.9.1 Patient characteristics

The following patient characteristics need to be documented to describe the study population.

- Age in years;
- Sex;
- Pregnancy status (see Section 3.9.11);
- Smoking history (see Section 3.9.12);
- Healthcare worker status (see Section 3.9.13);
- Occupation (optional);
- Ethnic group (optional);
- SES/deprivation (optional).
- Each study site/country to describe community measures in place to limit exposures.

3.9.2 Clinical characteristics (symptoms and markers of severity)

Collection of good quality symptom information is crucial for VE studies to be able to validate the case definition used (see section 3.5). If only CVE is estimated, the following clinical characteristics and markers of disease severity should be collected:

- fever or feverishness;
- cough;
- shortness of breath.

In addition, study sites may collect the following **additional** symptoms for CVE, which are associated with COVID-19 illness and are part of ECDC's COVID-19 case definition:

- anosmia;
- ageusia;
- dysgeusia.

In addition, for study countries participating in IVE estimation, information on the following **additional** symptoms for IVE should also be collected:

- headache;
- sore throat;
- myalgia;
- malaise:
- deterioration of general condition (asthenia, weight loss, anorexia).

The following symptoms are **optional** for the hospital-based CVE study:

- coryza, rhinitis;
- sore throat:
- · chest pain;
- chills;
- fatigue;
- nausea;
- vomiting;
- abdominal pain:
- diarrhoea:
- conjunctivitis:
- confusion:
- dizziness:
- tachypnoea or other signs of low oxygen saturation (restlessness);
- rash or other dermatological manifestation;
- palpitations/rapid heartbeat.

The following information can be used to indicate severity when measuring CVE to prevent severe disease:

- oxygen use;
- ICU admission;
- invasive ventilation;
- death.

Study sites should also collect information on:

date of first key symptom onset.

3.9.3 Information on swab and test results

For each patient, sites will collect information on:

- date of admission (to allow estimation of and stratification by time from onset to hospitalisation, and to measure length of hospital stay);
- date of discharge/death (to allow the length of hospital stay to be measured);
- date of swab or date sample obtained (to allow estimation of and stratification by delay from swab to onset);
- information on COVID-19/influenza test(s) performed and laboratory results:
 - type of influenza and/or COVID-19 test (PCR, rapid test)
 - result of influenza and/or COVID-19 test
 - including information on antigenic and genetic analysis, if available

Some studies will be carrying out testing for other respiratory viruses. Study sites can collect:

 test results from any other respiratory viruses (e.g. rhinovirus, RSV, enterovirus, adenovirus, human metapneumovirus, seasonal coronaviruses, etc.)

3.9.4 Pre-existing chronic conditions

SARI patients (in particular, those who are ultimately included as controls) with underlying conditions may be included due to an exacerbation of these conditions, unrelated to SARI. These patients may be more likely to be infected with SARS-CoV-2/influenza, or to develop more severe disease than the source population. Furthermore, these patients may be more likely to be vaccinated against COVID-19/influenza than the source population and the CVE/IVE may therefore be underestimated. The presence of underlying conditions will be documented among all recruited SARI patients.

Underlying conditions which could be potential confounding factors/effect modifiers are shown in Table 4 (for their ICD codes, see Annex 4).

Table 4. Recommended and optional pre-existing conditions as potential effect modifiers or confounding factors

Recommended	Optional
Asthma	Anaemia/chronic haematologic disease
Immunodeficiency (including HIV infection) and organ transplant	Asplenia
Cancer (solid organ and haematological)	Chronic liver disease/cirrhosis
Diabetes mellitus	Dementia
Heart disease (excluding hypertension)	Neuromuscular disorders
Hypertension	Renal disease (exclude acute renal failure)
Lung disease (excluding asthma)	Rheumatologic diseases
Obesity or	Stroke
height and weight, or	Tuberculosis
BMI ⁸ (sites to include whichever is feasible/available)	

- Each study site/country to keep a list to include pre-existing conditions defining target groups for vaccination in their country.
- Each study site/country to define the list of chronic conditions to be included and state whether they are used to define target groups for vaccination, as well as any pre-existing medications being taken.

3.9.5 Severity of underlying condition/healthcare utilisation

The severity of an underlying condition could be an effect modifier or a confounding factor (i.e. not just presence of underlying condition). To document and control for healthcare-seeking behaviour in control groups and the severity of the underlying conditions, information will be collected on the number of hospital admissions due to underlying conditions in the 12 months prior to inclusion in the study.

3.9.5 Ethnicity

Documentation of the ethnicity remains optional. Some studies have shown that certain ethnic groups may be at higher risk, either of becoming infected with SARS-CoV-2, or of developing severe COVID-19. Uptake of, or access to vaccination may also be linked to ethnicity. Not all sites/countries collect, or are able to collect, this information. Even if all sites /countries were able to collect information on ethnic group, each group may be defined differently in different countries. The definitions for each ethnic group will need to be standardised across study sites before this information can be collected robustly and used to investigate CVE by ethnic group for pooled data. However, any site(s)/countries which can or do already collect this information may find it useful for examining their national CVE estimates by ethnic group.

Each study site/country to indicate whether they can or do collect information on ethnic groups, and define their ethnic groups and (proposed) method of collecting the data (e.g. by self-reported ethnicity, from patient notes, or any other method).

3.9.6 Vaccination status – vaccines other than influenza/COVID-19

Study sites can collect (if desired) information on pneumococcal disease (pneumococcal polysaccharide vaccine (PPV) and pneumococcal conjugate vaccine (PCV)), respiratory syncytial virus (RSV; once available) and/or other relevant vaccinations. In particular, RSV vaccination may be of relevance for IVE/CVE studies if uptake is good and it has been recommended to similar target groups as the influenza/COVID-19 vaccine. Vaccination status variables could include the following for each disease (pneumococcal/RSV/other):

- vaccination status;
- type of vaccine;
- number of doses;
- either date or year of vaccination where available.

For study countries that are **not** participating in IVE, information on previous influenza vaccination (including date of vaccination) will also be collected.

Each study site/country to document other vaccination status variables collected in their IVE and CVE studies.

3.9.7 Medication status for chronic condition(s)

The use of specific types of chronic medications prior to vaccination or illness may modify or confound the effect of the vaccine. For influenza, data on statin use should be collected otherwise the documentation of the medication status remains optional.

⁸ Obesity defined as BMI>29.

Definition of medication status for pre-existing chronic condition(s):

- An individual is considered as 'on medication' if he/she has received the medication at least once during the six months before:
 - the first dose of pandemic COVID-19 vaccination (if date of medication use available: for the analysis measuring the effect of chronic medications on CVE);
 - onset of SARI symptoms (for unvaccinated individuals: for the analysis measuring the effect of chronic medications on COVID-19);
 - hospitalisation.
 - An individual is considered as 'not on chronic medication' if he/she did not receive medication before
 the periods specified in the protocol above to document such medication use.

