outcomes			2 = discharged from hospital	known at the time of data collection (note: this may be updated later)
			3 = still on treatment	(updated to match TESSy)
			8 = unknown outcome	

	Variable	Туре	Values and coding	Definition
	outcomedate	Date (dd/mm/yyyy)		Date of outcome
	icu	Numeric (categorical)	0 = No	Admission to intensive care unit (ICU)
			1 = Yes	or high-dependency unit (HDU)
			8 = Do not know	
	icuadmitdate	Date	dd/mm/yyyy	Date of ICU/HDU admission
	numberdaysicu	Numeric		Number of days in ICU/HDU
	resp_support	Numeric (categorical)	0 = None	Level of respiratory support
			1 = High-flow oxygen therapy (non- invasive ventilation)	
			2 = Invasive ventilation	
			3 = Extra corporeal membrane oxygenation (ECMO)	
			4 = Other	
			8 = Do not know	-
	hospitalward	Numeric (categorical)	0 = Special COVID-19 ward	First ward of referral (NOTE: this may
			1 = Lung, pulm/respir.	alternatively be sent as text, as for influenza)
			2 = Internal medicine	_
			3 = Infectious diseases	
			4 = Emergency or A&E	
			5 = Cardiology	
			6 = Geriatric	
			7 = ICU or HDU	
			9 = Other	
			10 = Obstetrics/gynaecology	
			11 = Surgery	
			12 = Paediatric	
			8 = Do not know	
	hospitalward_oth	Text		Specify other ward
Section D Pre-existing chronic	asthma	Numeric (categorical)	0 = No	Asthma
conditions			1 = Yes	
			8 = Do not know	
	cancer	Numeric (categorical)	0 = No	Cancer (any)
			1 = Yes	_
			8 = Do not know	
	heartdis	Numeric (categorical)	0 = No	Heart / cardiac disease (excluding hypertension)
			1 = Yes	-
			8 = Do not know	
Section D continued	lungdis	Numeric (categorical)	0 = No	Chronic lung disease (excluding asthma)
			1 = Yes	,
			8 = Do not know	
	diabetes	Numeric (categorical)	0 = No	Diabetes
			1 = Yes	_
			8 = Do not know	
	hypert	Numeric (categorical)	0 = No	Hypertension

	Variable	Туре	Values and coding	Definition
			1 = Yes	
			8 = Do not know	
	immuno	Numeric (categorical)	0 = No	HIV or other immunodeficiency
			1 = Yes	disorders including organ transplantation
			8 = Do not know	
	obese	Numeric (categorical)	0 = No	Obesity (only if height, weight and BMI
			1 = Yes	not collected; can be calculated)
			8 = Do not know	
	hosp_visit	Numeric (integer)		Number of times patient was admitted to hospital for an underlying chronic condition in the 12 months prior to current admission
Section E	statin_pre	Numeric (categorical)	0 = No	Patient was on statins since or from 01
Medications for chronic medical			1 = Yes	Sept 2022
conditions			8 = Do not know	

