- use of medications for chronic conditions (e.g. statins, for IVE);
- Other stratifications may be included.

Virus variant-specific outcomes will be used, if available and feasible at the time of analysis.

A sufficient sample size should be planned in order to ensure enough individuals in each stratum for a precise estimate. Effect modification will be assessed comparing the OR across the strata of the potential effect modifiers. Confounding will be assessed by comparing crude and adjusted OR for each potential confounder.

Multivariable analysis

A multivariable logistic regression analysis will be conducted to control for negative and positive confounding. Odds ratios and standard errors will be obtained. Variables will be tested for multicollinearity. Interactions will be tested using the likelihood ratio test or Wald's test and will be included in the model if significant at the 5% level. Factors other than statistical significance (prevalence of exposure, magnitude of OR) will also be used as criteria for inclusion of a variable or an interaction term. If possible, a variable for sex, age and onset time should always be included in the model.

Continuous variables

Continuous variables in the COVID-19/influenza datasets include age, time of onset of symptoms, and hospitalisations in the past 12 months. These variables can be coded as categories (e.g. age group, week of symptom onset, etc.) However, when coding continuous variables as categories, information may be lost, or introduce residual confounding and increase the standard error of the model. Tests will be carried out to see if these variables could be coded as a linear term, polynomial or a spline. In addition, a balance will be sought between simplicity of a model (so a non-expert can understand it), precision and a model that estimates the vaccine effect with the least bias.

Identifying heterogeneity, testing for heterogeneity

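### Chronic medication status rests on three unranked windows, a definition of non-use that is not the complement of use, and a fixed 2022 statin date that breaks the six-month rule

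*Protocol*

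**What the plan says.** Section 3.9.7 gives the reason for collecting medication: "The use of specific types of chronic medications prior to vaccination or illness may modify or confound the effect of the vaccine". On what is collected it says: "For influenza, data on statin use should be collected otherwise the documentation of the medication status remains optional".

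Under "Definition of medication status for pre-existing chronic condition(s", a patient is on medication if "he/she has received the medication at least once during the six months before" one of three events:

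- for the question of effect modification, "the first dose of pandemic COVID-19 vaccination (if date of medication use available: for the analysis measuring the effect of chronic medications on CVE";
- in patients who are unvaccinated, the start of the SARI illness, for a separate analysis of how medication relates to COVID-19 itself;
- hospitalisation, with no restriction by vaccination status or by analysis.

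Nothing says which anchor applies when more than one could. The same section defines a patient as not on chronic medication when there was no receipt before the specified periods, rather than during them.

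Annex 1, Section E, defines the statin variable (statin_pre) as "Patient was on statins since or from 01" Sept 2022. The chronic-medication variables there are yes/no/do not know or free text, with no dates of use. Annex 2, under Stratified analysis, lists "use of medications for chronic conditions (e.g. statins, for IVE" among the strata, depending on sample size.

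**The concern.** Section 2.3 and the seasonal definitions in section 3.8.1 make the dose of the current campaign the main CVE exposure, and section 3.3 names autumn 2023. The medication rule still refers to the first pandemic dose. Section 1.1 says vaccination campaigns had started in all EU/EEA countries by January 2021, so for many patients that window would close years before the illness under study. For unvaccinated individuals the listed anchor is current onset.

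If a modifier is measured at different times in the exposed and the reference group, part of any difference in effectiveness between users and non-users comes from the measurement. For influenza vaccine effectiveness (IVE), statins are the one medication sites are expected to record and the one Annex 2 names as a stratifier. Their coding in the minimum dataset does not follow the six-month rule.

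**Working it through.** The plan gives no figure on this point, so there is none to reproduce. The check sets the definitions side by side, counts months, and sizes the possible bias with assumed inputs.

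**1. The anchors against the exposure.**

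| Anchor in 3.9.7 | Restricted to | Stated purpose | Can it be built from Annex 1? |
|---|---|---|---|
| First pandemic dose | Patients with dated medication use | Effect of medication on CVE | No; medication dates are not listed |
| SARI onset | Unvaccinated individuals | Effect of medication on COVID-19 | Not specified; no medication dates |
| Hospitalisation | No one | None stated | Yes, as a question asked at admission |

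Section 3.8.1 has two meanings of unvaccinated: never vaccinated (or vaccinated on or after onset) in the general definitions, and no dose in the campaign of interest, whatever came before, in the seasonal ones. A patient with earlier doses but no campaign dose has a first pandemic dose and is also seasonally unvaccinated. Section 3.9.7 does not say which window that patient takes.

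**2. Use and non-use are not complements.** Take the hospitalisation anchor. A patient whose first receipt was three months before admission is a user (receipt inside the window) and also a non-user (no receipt before the window). A patient whose last receipt was nine months before admission is neither. The same happens under every anchor.

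**3. Months.**

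- Statin look-back: 1 Sept 2022 to 1 Oct 2023 = 13 months; to 1 Jan 2024 = 16 months; to 19 May 2024 (end of week 20) = 20.6 months. The rule in 3.9.7 is six. If the code means any use since that date, a patient who stopped statins in October 2022 and is admitted in January 2024 (15 months later) is coded as a user in Annex 1 and is not one under the six-month rule.
- First-dose window: assuming first doses between 1 January and 31 December 2021, it closes 21 to 33 months before 1 October 2023 and 28.6 to 40.5 months before 19 May 2024.

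**4. Size of bias if the windows differ by exposure group.** All inputs are assumed: coverage 50%; true current medication use p = 30% or 50%; use unrelated to vaccination; medication misclassified in the vaccinated only, with sensitivity Se and specificity Sp of the first-dose window against current use; medication–case odds ratio M.

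Let c1, c0 be vaccinated controls on and off medication, and a1, a0 the corresponding cases. The observed counts are:

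- A1 = a1·Se + a0·(1−Sp) and A0 = a0·Sp + a1·(1−Se), with C1 and C0 formed from c1 and c0 in the same way.
- With b and d the unvaccinated cases and controls, OR1 = (A1/C1)/(b1/d1) and OR0 = (A0/C0)/(b0/d0). The ratio of odds ratios is OR1/OR0.

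Example: p = 0.3, VE 50% in both strata, M = 2, Se = 0.7, Sp = 0.95.

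- c1 = 0.15, c0 = 0.35, a1 = 0.15, a0 = 0.175, b1/d1 = 2, b0/d0 = 1.
- A1 = 0.105 + 0.00875 = 0.11375; C1 = 0.105 + 0.0175 = 0.1225; OR1 = 0.9286/2 = 0.464 (VE 54%).
- A0 = 0.16625 + 0.045 = 0.21125; C0 = 0.3325 + 0.045 = 0.3775; OR0 = 0.560 (VE 44%).
- Ratio = 0.83, where the truth is 1.00.

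Observed ratios over both values of p and M = 1.0, 1.5 and 2.0:

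| Se / Sp | True ratio 1.00, M = 1.0 | True ratio 1.00, M = 1.5 | True ratio 1.00, M = 2.0 | True ratio 1.50 (VE 40% on, 60% off), all M |
|---|---|---|---|---|
| 0.9 / 0.97 | 1.00 | 0.95–0.96 | 0.90–0.92 | 1.24–1.43 |
| 0.7 / 0.95 | 1.00 | 0.87–0.90 | 0.78–0.83 | 0.97–1.35 |
| 0.5 / 0.90 | 1.00 | 0.80–0.82 | 0.68–0.71 | 0.78–1.22 |

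With one common window (Se = Sp = 1 in this model) the true values return.

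**The case against.** A reader might infer that medication is always measured around 2021 in vaccinated patients and at onset in unvaccinated ones, so that modification of effectiveness by medication cannot be estimated. The documents do not support that, for five reasons.

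- Hospitalisation is a listed anchor without restriction and gives every patient one common window.
- The first-dose anchor applies only where medication dates exist. Annex 1 has none, so on the minimum dataset the differential miscoding does not arise; it needs a site that holds dates.
- The first-dose and onset anchors are attached to different analyses. No sentence tells the analyst to combine them in one model.
- In Table 3, two of the four reference groups consist wholly of previously vaccinated people, and the overall comparison can include them. They also have a first dose, so that anchor would give both groups the same kind of window, though an old one. The contrast is sharpest in the comparison with never-vaccinated patients.
- The statin date is the same for everyone, so it creates no difference between exposure groups.

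All five stand, and they limit the point. They do not remove it. The common anchor is unranked and tied to no analysis, while the only anchor named for the CVE-modifier question is the outdated one. The non-use definition fails under any anchor. The statin code contradicts the six-month rule whatever the exposure. It is also fair that medication other than statins is optional, that sites may use their own coding, and that the stratification depends on sample size.

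**Conclusion.** The point holds as an inconsistency among definitions the protocol itself fixes. The anchors are unranked, the first-dose anchor does not fit the seasonal exposure, non-use is not the complement of use, and the statin look-back is 13 to 16 months for October 2023 to January 2024 admissions instead of six. The fault of the statin date is inconsistency and staleness, not dependence on exposure.

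The consequence is confined to the secondary effectiveness-by-medication strata, which may be biased or not comparable across sites. Primary CVE and IVE are not shown to be affected. If differential windows were used, the bias would be small for stable medication (ratio 0.90–1.00 for a true 1.00 at Se 0.9) and absent with no true modification when medication is unrelated to case status. It could hide or reverse a true ratio of 1.50 when use changes a lot and is linked to case status. These sizes rest on assumed coverage, prevalence, Se, Sp and M. The first-dose gaps rest on assumed 2021 dates, since the protocol gives only the start of campaigns.

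**What to change.** In section 3.9.7, state one window for all patients whatever their vaccination status: at least one receipt in the six months before hospitalisation, an anchor already listed. Define not on medication as no receipt in that same window. In Annex 1, replace the fixed 01 Sept 2022 in statin_pre with that window, so that the Annex 2 stratum uses the same definition.

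The cost is a wording change in one section and one variable definition. The downside is that statin data already coded with the old date are not directly comparable with data coded under the new rule.

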3.9.8 Antiviral administration

The use of antivirals pre-hospitalisation should be documented: type, dosage (if possible) and date of administration (patients receiving antivirals two weeks prior to swabbing will be excluded from CVE/IVE analyses), as this may lead to misclassification biases.

Each study country to list any antivirals administered prior to hospitalisation.

3.9.9 Previous SARS-CoV-2/influenza infection

Individuals who have been previously infected may have a greater response to the vaccine or be less likely to be reinfected, even if unvaccinated. Previous infection may impact the probability of receiving a COVID-19 vaccine (e.g. if the perception of risks associated with a new SARS-CoV-2 infection differs by previous infection status) and the risk of infection (due to immunity conferred by past exposure to SARS-CoV-2) [28]. Therefore, confounding of CVE by previous infection status may arise. Previous infection status may also be an effect modifier, as COVID-19 vaccination may provide greater absolute benefit to people without pre-existing immunity [29].

If possible, study sites will collect the following information:

- whether the patient had a previous positive SARS-CoV-2 test(s) (yes/no/unknown)
- optional:
 - type(s) of test: PCR, rapid test (in case of multiple positive test results, the most recent)
 - date(s) of test (in case of multiple positive test results, the most recent)
 - history of COVID-19, e.g., clinical confirmation.

If all study sites collect information on previous SARS-CoV-2 infection, the following analyses will be conducted with the pooled data. Otherwise, these analyses will be conducted in the subset of sites that collect this information. In the primary analysis, patients testing SARS-CoV-2 positive in the previous 60 days will be excluded from the analysis (this will avoid including cases who test positive due to prolonged shedding of a given illness episode and avoid including controls who are not at risk of being a case, according to the ECDC reinfection definition) [28]. Separate sensitivity analyses could be carried out including controls who recently tested SARS-CoV-2 positive, adjusting CVE estimates for previous SARS-CoV-2 infection, or stratifying CVE estimates by previous SARS-CoV-2 infection, if sample size allows. Additionally, if sample size allows and information is available, controls previously infected with SARS-CoV-2 will be included or excluded depending on number of days since last infection (to be explored in sensitivity analyses), or variant of infection.

Each study site/country to collect and describe measure(s) used to capture prior SARS-CoV-2/influenza infection.

